Our primary outcome analyses are consistent with the CONSORT Statement on Reporting of Noninferiority and Equivalence Randomized Trials.⁸¹ The sample size was calculated using the Non-Inferiority Test module available in the statistical software PASS 2008. The calculation was reviewed by the study statistician, [name]. To ensure that the AI-CBT program retains a clinically acceptable effect, the non-inferiority margin was set at 2 points on the Roland Morris Disability Questionnaire (RMDQ).⁷⁴ A two point difference (or difference in reduction) in the RMDQ is considered to be a minimally clinically significant effect.⁸² The power calculation was based on a significance level of 0.025, with a power of 90%, when postulating a true difference in group means of 0 and a standard deviation of the outcome of 4.5 in both groups. Specifically, if we denote by D the true difference in mean RMDQ scores (at 12 weeks) between the AI-CBT and standard CBT groups, with the non-inferiority margin set at 2, we plan on testing the null hypothesis $H_0: D \geq 2$ versus the alternative hypothesis $H_1: D < 2$, which amounts to a one-sided, two-sample t-test. Thus, if the null hypothesis is rejected, it can be concluded that AI-CBT is non-inferior to CBT. We will test this hypothesis at a one-sided .025 significance level based on a confidence level where we will reject the null hypothesis when the upper bound of the two-sided 95% confidence interval for D is less than 2. To ensure that the AI-CBT algorithm has as much information as possible to learn quickly how best to tailor patients’ course of therapy, we will disproportionately randomize patients to the AI-CBT group in an allocation ratio of 1.37:1 for the AI-CBT: standard CBT groups, respectively. Assuming this ratio, we will have 90% power to detect non-inferiority with a total sample size of 221 patients, or 128:93. To account for a 20% drop-out rate in both groups, we will enroll 277 patients (160 in the AI-CBT group, 117 in CBT group).

Randomization

After completing baseline assessments, patients will be randomized to AI-CBT or standard telephone CBT by the research staff. The randomization sequence and opaque randomization envelopes for recruiters will be generated prior to recruitment by the study statistician using a random number generator. Analysts and the investigators will be blinded to patients’ group assignment until initial outcome analyses are completed. To ensure balance across treatment arms in potential modifiers of intervention effect, randomization will be conducted within blocks defined by site (Michigan versus Connecticut) and patient age (<65 vs. ≥ 65).

Description of Data Collection

Overview. We have selected outcome measures based on recommendations from the Initiative on Methods, Measurement, and Pain Assessment in Clinical Trials (IMMPACT) recommendations.^{72,73} Endpoint measures are consistent with CONSORT guidelines recommending that non-inferiority trials use outcomes similar to those used in efficacy studies. In addition to primary and secondary outcomes (defined below), we will examine treatment satisfaction, treatment credibility, patient engagement and dropout, and goal accomplishment. Process and outcome data will be collected via the following sources: **Patient Surveys**: Baseline, three-month, and six-month surveys will be conducted via telephone by trained research assistants. **Qualitative Interviews**: These will be conducted with purposive samples of patients in the AI-CBT group at follow-up. We will target patients who demonstrate significant improvement, patients who were very satisfied with AI-CBT, patients without significant improvement, patients who were

dissatisfied, and patients who dropped out of the intervention. Additional qualitative interviews will be conducted at follow-up with CBT therapists and PACT team members. CBT Therapist Logs: Logs will be used to track therapist time spent in patient treatment, attempting to reach patients, and key information about those interactions. IVR: The AI-CBT IVR system will capture information about intervention patients' pedometer-measured step-counts, pain related functioning, CBT skill practice, and missed data reporting. Administrative and Clinical Data Systems: These will be used to track patients' use of other VA inpatient and outpatient services for pain management, mental health, and medical care.

Primary Outcome. The 24-item Roland Morris Disability Questionnaire (RMDQ) is an IMMPACT endorsed measure⁷³ of pain-related disability for persons with chronic low back pain. Strong evidence supports the RMDQ's reliability, validity, and responsiveness to change during trials.⁷⁴

Secondary Outcomes. Global Pain Intensity will be assessed using the Numeric Rating Scale (NRS-I) an IMMPACT-recommended 11-point numeric rating scale of pain severity.⁷² Pain-Related Interference will be measured using the 9-item Interference subscale of the West Haven-Yale Multidimensional Pain Inventory (WHYMPI).⁶⁶ This IMMPACT-recommended measure assesses pain-related interference in daily activities and has demonstrated good internal consistency.⁷² Depression Symptom Severity will be assessed using the 21-item Beck Depression Inventory (BDI), a widely used measure with excellent internal consistency and stability.⁶⁰ The Patient Global Perception of Change scale is a single item measure that quantifies a participant's overall perception of improvement since beginning treatment and the clinical importance of that improvement. Participants indicate improvement on a 7 point "much worse" to "much better" scale. This is a well-validated measure recommended by IMMPACT.⁷³ Finally, we will use the Veterans SF-12 to assess health-related quality of life. This measure has demonstrated good internal consistency and is strongly correlated with socioeconomic status and morbidities.⁷⁵

Resource Use (Aim 2). Intervention Costs. Therapists will use a log to record time spent in intervention-related activities for a random 20% of all treatment days. Time records will be combined with wage data from the VA Financial Management System to estimate intervention-specific personnel costs. Technology costs of the AI-CBT program include fixed costs (e.g., software development and computer maintenance) plus variable costs (e.g., minute costs for IVR calls). One-time fixed start-up costs will be reported separately. VA Inpatient and Outpatient Service Use data will be obtained from the Musculoskeletal Diagnoses Cohort (MSD), a project currently underway as part of the VA Connecticut Healthcare System's CREATE. The MSD is developing validated algorithms for using VA electronic health record data to identify utilization events, comorbid conditions, receipt of opioid medications, and pain screening results, for patients with pain-related diagnoses. Information on non-VA admissions will be collected by the patient survey. To mitigate recall bias, we will use a two-time frame method that asks about utilization over the past 6 months and over the past 2 months with more weight given to the shorter timeframe.⁷⁶

Treatment Satisfaction and Engagement (Aim 3). For patients in the AI-CBT group, we will calculate IVR adherence as we have in the past,⁴⁹ i.e., as the proportion of days during which an assessment was attempted in which one was successfully completed and the number of weeks during which the patient completed at least four out of seven requested IVR reports. Participants' judgments of Treatment Credibility will be assessed using a reliable questionnaire adapted from Borkovec and Nau.⁷⁷ Treatment credibility has been shown to be significantly associated with treatment satisfaction, engagement in treatment, and number of sessions attended. The Pain Treatment Satisfaction Scale of the Patient Outcomes Questionnaire will be used to assess patient satisfaction with various domains of pain care.⁷⁸ This 5-item measure shows good internal consistency and significant associations with staff and patient ratings of patient improvement. Attendance in "Live" Telephone CBT Sessions and Program Dropout In order to understand reasons for treatment dropout, we will attempt to reach samples of patients with low levels of engagement for qualitative interviews. Participants will rate their Continued Skill Use at follow-up for each of the target behaviors emphasized in the CBT program on a 0 (not at all accomplished) to 10 (completely accomplished) scale. As described above, Daily IVR calls will be used to collect data in the AI-CBT condition regarding pedometer measured step-counts, CBT skill practice, and pain-related functioning using pre-recorded questions we have used successfully in our prior studies.

Interim Data Analysis

There are currently no plans for interim data analysis.

Handling Missing Data

Approach to Missing Data. If more than 15% of a covariate is missing, we will use multiple imputation methods based on the SAS MI Procedure. We will check if the pattern of missingness is monotonic (i.e., if patients missing data at 3 months also have missing data at 6 months) and use a Markov chain Monte Carlo method that assumes multivariate normality to impute missing values. We will impute five sets of data and combine the imputed results using the SAS MIANALYZE procedure to obtain a valid estimate of the confidence limit and treatment effect.⁸⁵ When data are missing for items within scale scores, we will use recommended imputation procedures rather than deleting patients list-wise from the analysis.

Definitions of Covariates

Demographics and Other Covariates Measured at Baseline. We will measure patients' baseline Sociodemographic and Pain Characteristics that have been shown to be associated with treatment outcomes, e.g., age, gender, education level, racial/ethnic background, marital status, occupational status, pain duration, and number and location of pain sites. We also will gather data on participants' level of health literacy.⁷⁹ Pain Classification will be derived through a systematic evaluation of each enrolled participant's EMR using an assessment tool based on clinical guidelines for diagnosing and treating low back pain.¹ Pain classes will include non-specific low back pain, low back pain with a radicular component, or low back pain associated with other specific spinal causes. A nurse practitioner, who is supported by the West Haven COIN and who has been trained to use this tool and is using it in our trial IIR 09-058, will conduct the assessment. She will be supervised by a pain medicine physician ([name]) who will review ten percent of the classification ratings for accuracy and provide corrective feedback if necessary. Psychiatric and Substance Abuse Comorbidities will be measured using medical record diagnoses and mental health encounters. Additional self-report information will be collected using subscales of the Mini International Neuropsychiatric Interview (MINI)⁶¹ related to mood and substance abuse disorders. Pain Medication Use will be assessed through patient survey and a review of computerized pharmacy records. Pain medication will be coded as non-steroidal anti-inflammatory, non-narcotic analgesics, narcotic analgesics, and benzodiazepines and other sedative/hypnotics. For each category, we will document post-treatment whether patients have experienced an increase, no change, or decrease in their medication use. Distance from VA will be calculated and used as a measure of geographic access. The Pain Catastrophizing Scale is a 13-item self-report scale that examines thoughts and feelings people may experience when they are in pain including rumination, magnification, and helplessness.⁸⁰ Finally, Pain-related Fear will be measured using the Tampa Scale of Kinesiophobia-revised (TSK-R), which has two subscales (Fear of Harm/Activity Avoidance and Pathophysiological Beliefs) and has been shown to be sensitive to treatment-related change.

Methods for Dealing with Data Transformations

We will examine the distribution of all study variables to assess extreme values, missing data, variances, skewness, and type of distribution. Preliminary analyses will examine the distributions of variables to assess deviations from normality and other deviations from assumptions of the planned statistical analyses. Outliers will be corrected. Transformations of the data will be conducted if appropriate to obtain normality of residuals.

Definitions of the Analytical Sets

Baseline Comparability, Reach, and Representativeness. We will examine baseline differences across

groups in measures of study endpoints as well as other potential prognostic indicators, such as patients' age, comorbid diagnoses, and history of pain treatment. Any differences across groups in baseline characteristics will be controlled statistically in analyses comparing outcomes. The RE-AIM framework is a methodology for systematically considering all strengths and weaknesses of an intervention in order to better guide program planning.⁸³ To evaluate reach, we will ask patients who decline study participation whether they would be willing to provide informed consent to participate in a brief survey that identifies their reasons for declining participation and the characteristics that differentiate them from enrollees.

Analysis of Endpoints (addressing Specific Aim 1). We will test for non-inferiority of AI-CBT compared to standard telephone CBT at 12 weeks by comparing the upper limit of the two-sided 95% confidence interval for the difference in the mean RMDQ scores, calculated as AI-CBT minus standard CBT, to the pre-set non-inferiority margin of 2 points in RMDQ and will conclude that AI-CBT is non-inferior if the upper limit is less than 2. Because intent-to-treat analysis can raise the risk of type I error in a non-inferiority trial,⁸¹ we will conduct both a per protocol and intent-to-treat analysis. The "per protocol" group assignment will be defined as completing four or more CBT sessions (either IVR or "live" sessions); however, we will revisit this definition with the Expert Panel prior to the start of the trial. We will declare AI-CBT non-inferior to standard CBT only if AI-CBT is shown to be non-inferior using both the intention-to-treat and per-protocol analysis sets. We expect that RMDQ scores will be normally distributed. If not, we will use transformations to achieve normality. We also will develop a two-level linear mixed-effects model that uses RMDQ follow-up scores at both assessment times (three and six months) as the dependent variables; treatment group, time and the treatment by time interaction as categorical explanatory variables; and baseline RMDQ score as a continuous covariate. If this model shows no significant time by group effect, we can drop the interaction term and test for the time-averaged non-inferiority of AI-CBT compared to standard CBT between 3 and 6 months. This model will also allow for adjustment for design-related factors (e.g., site and age). An unstructured variance-covariance matrix will be used to model the error variance. Secondary outcomes including pain intensity, emotional functioning, global perception of change, and quality of life will be analyzed in a manner similar to that used for the primary outcome. Analyses of all other outcomes will be conducted on an intent-to-treat basis.

Intensity of Service Use (Specific Aim 2). We will compare service utilization by category (e.g., CBT therapist time, PCP visits, and pharmacy use) between groups. We will conduct a budget impact analysis⁸⁴ and will include the cost of the intervention (personnel, supplies, CBT therapist training, and IVR fixed/variable costs) as well as costs for specific medical care services likely to be affected. Data from CBT therapists time records will be combined with wage data from the VA Financial Management System to produce estimates of intervention-specific personnel costs. Costs associated with the use of specific medical care services, such as medications, will be obtained from the Decision Support System (DSS) files. Cost analysis will be conducted in accordance with the guidance provided by Mauskopf et al.⁸⁴ including the use of sensitivity analysis and scenarios that allow for varying assumptions about intervention uptake, compliance or component costs. All resource use and cost comparisons will be adjusted for any observed differences in baseline characteristics. Because costs of resource utilization are usually skewed, alternative modeling techniques (e.g., log-transformed costs, negative binomial regression) will be used.

Intervention Engagement and Satisfaction with Care (Specific Aim 3). As in our prior research,⁴⁹ we will conduct extensive analyses of the process of intervention delivery in both arms. We will monitor the proportion of telephone CBT sessions that are completed, and we will determine the patient and session characteristics associated with patients' reports of skill practice. Patients in the AI-CBT group will report their satisfaction with aspects of the intervention (e.g., whether it provided information useful for achieving behavioral targets), and we will assess the correlation between satisfaction ratings and measures of: intervention engagement, patients' baseline characteristics, and changes in pain-related functioning. Differential dropout across groups will be examined using Kaplan-Meier curves and survival models.

Preplanned Subgroup Analysis. Because AI-CBT will continue to learn patterns in patients' experience throughout the intervention period, we hypothesize that the second 50% of patients randomized will show

an even larger difference in clinician time than the first 50%, while still demonstrating non-inferiority in pain-related outcomes. Differences in pain related functioning and in clinician treatment time across treatment groups will be tested in this subgroup analysis after stratifying the sample into early versus later recruits.

Mediators and Moderators of Intervention Effects. We will use multivariate modeling to identify the mechanisms through which the intervention achieves effects on outcomes and differential effects across subgroups.⁸⁶ Initial models will include only treatment group as the predictor. Subsequent nested models will introduce potential mediators (such as the number of completed therapist sessions), and we will evaluate changes in the relationship between experimental condition and outcomes before and after covariates are introduced. Analyses of effect moderation will focus on baseline pain severity and comorbid diagnoses using standard approaches to evaluate interactions between these covariates and patients' experimental condition.⁸⁶ Significant interactions will be interpreted by plotting regression lines for predicted outcomes of patients with high and low values of the moderator.

Evaluating the Reliability of Patients' IVR Reports. We will evaluate the integrity of IVR-reported step counts and functioning by examining associations between IVR reports and baseline characteristics that the literature suggests would be associated with patients' functioning (e.g., baseline SF-12 scores, comorbid medical diagnoses, and age). We also will examine serial correlations across IVR reports under the assumption that all correlations between scores and proximal scores should be positive and roughly of equal magnitude controlling for the time difference between reports.

RE-AIM⁸³ Dimensions of Intervention Adoption, Implementation, and Maintenance. Adoption will be evaluated by examining variation in study participation and intervention engagement across sociodemographic and clinical subgroups of eligible patients. For example, we will determine whether older patients or those with less education have more difficulty responding to queries about their step counts or pain-related functioning via IVR. Adoption at the provider level will be monitored by recording the proportion of providers who are willing to have their patients participate and providers' reasons for not participating. Implementation and maintenance will be evaluated through semi-structured questions at follow-up designed to identify program characteristics that might be a barrier to patients' use of the intervention in other settings and the intervention characteristics that patients feel would make it more valuable to others with chronic pain. We also will meet with clinicians in each site to gauge their willingness to adopt and maintain a similar intervention, and the ways such a system can be designed to best complement existing services.

Qualitative Interviews and Mixed-Methods. We will use audio-taped interviews with patients, CBT therapists, and PACT team members to provide a context for interpreting intervention effects and suggest additional subgroup analyses. Interviews will be transcribed verbatim, and we will enter the transcripts into NVivo for file storage and selective retrieval. Using accepted techniques,⁸⁷ Drs. [name] and [name] will independently read transcripts, approaching the data with analytic categories in mind, but identifying other categories in the data. An iterative process will be used until agreement is reached on categories and their definitions, after which we will develop a coding template and enter it into NVivo as a tree diagram.

List of Adverse and Serious Adverse Events to be Monitored

We will track all events which our local IRB defines as potentially adverse.

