Our primary outcome analyses are consistent with the CONSORT Statement on Reporting of Noninferiority and Equivalence Randomized Trials.⁸¹ The sample size was calculated using the Non-Inferiority Test module available in the statistical software PASS 2008. The calculation was reviewed by the study statistician, [name]. To ensure that the AI-CBT program retains a clinically acceptable effect, the non-inferiority margin was set at 2 points on the Roland Morris Disability Questionnaire (RMDQ).⁷⁴ A two point difference (or difference in reduction) in the RMDQ is considered to be a minimally clinically significant effect.⁸² The power calculation was based on a significance level of 0.025, with a power of 90%, when postulating a true difference in group means of 0 and a standard deviation of the outcome of 4.5 in both groups. Specifically, if we denote by D the true difference in mean RMDQ scores (at 12 weeks) between the

AI-CBT and standard CBT groups, with the non-inferiority margin set at 2, we plan on testing the null hypothesis $H_0: D \geq 2$ versus the alternative hypothesis $H_1: D < 2$, which amounts to a one-sided, two-sample t-test. Thus, if the null hypothesis is rejected, it can be concluded that AI-CBT is non-inferior to CBT. We will test this hypothesis at a one-sided .025 significance level based on a confidence level where we will reject the null hypothesis when the upper bound of the two-sided 95% confidence interval for D is less than 2. To ensure that the AI-CBT algorithm has as much information as possible to learn quickly how best to tailor patients' course of therapy, we will disproportionately randomize patients to the AI-CBT group in an allocation ratio of 1.37:1 for the AI-CBT: standard CBT groups, respectively. Assuming this ratio, we will have 90% power to detect non-inferiority with a total sample size of 221 patients, or 128:93. To account for a 20% drop-out rate in both groups, we will enroll 278 patients (160 in the AI-CBT group, 118 in CBT group).

D.9 Analysis

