Analysis of Endpoints (addressing Specific Aim 1). We will test for non-inferiority of AI-CBT compared to standard telephone CBT at 12 weeks by comparing the upper limit of the two-sided 95% confidence interval for the difference in the mean RMDQ scores, calculated as AI-CBT minus standard CBT, to the pre-set non-inferiority margin of 2 points in RMDQ and will conclude that AI-CBT is non-inferior if the upper limit is less than 2. Because intent-to-treat analysis can raise the risk of type I error in a non-inferiority trial,⁸¹ we will conduct both a per protocol and intent-to-treat analysis. The "per protocol" group assignment will be defined as completing four or more CBT sessions (either IVR or "live" sessions); however, we will revisit this definition with the Expert Panel prior to the start of the trial. We will declare AI-CBT non-inferior to standard CBT only if AI-CBT is shown to be non-inferior using both the intention-to-treat and per-protocol analysis sets. We expect that RMDQ scores will be normally distributed. If not, we will use transformations to achieve normality. We also will develop a two-level linear mixed-effects model that uses RMDQ follow-up scores at both assessment times (three and six months) as the dependent variables; treatment group, time and the treatment by time interaction as categorical explanatory variables; and baseline RMDQ score as a continuous covariate. If this model shows no significant time by group effect, we can drop the interaction term and test for the time-averaged non-inferiority of AI-CBT compared to standard CBT between 3 and 6 months. This model will also allow for adjustment for design-related factors (e.g., site and age). An unstructured variance-covariance matrix will be used to model the error variance. Secondary outcomes including pain intensity, emotional functioning, global perception of change, and quality of life will be analyzed in a manner similar to that used for the primary outcome. Analyses of all other outcomes will be conducted on an intent-to-treat basis.

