Chronic low back pain is one of the most common health problems among VA patients and is associated with emotional distress, substance abuse, suicide, and difficulty managing comorbid medical conditions. **Cognitive behavioral therapy (CBT)** is one of the most widely accepted, evidence-based approaches to pain management. Unfortunately, VA CBT programs are labor intensive, typically requiring 10 hour-long weekly sessions to teach self-management skills. Because of the scarcity of trained therapists and the high service costs, only half of Veterans receive care in a facility where pain CBT is offered. Where services are available, many Veterans drop out of treatment early, either because they experience minimal additional improvement after the first few sessions or because they simply cannot tolerate repeated in-person visits. Moreover, CBT quality may vary across therapists and patients due to the lack of a systematic method for monitoring Veterans' progress and personalizing treatment in light of their unique trends. Effective CBT programs vary widely in their program length and mode of delivery (in-person therapy, telephone, or even on-line), and it is likely that one size does not fit all patients' needs. For all of these reasons, the current VA delivery models are out-of-step with VA's patient-centered philosophy, and inconsistent with a stepped care approach designed to make service delivery more effective and efficient based on systematic evaluations of each patient's needs. As a result, current programs may expend scarce resources on some patients who could achieve equal benefit (or even greater benefit) from a more personalized approach that takes into account evidence regarding each Veteran's progress when planning subsequent sessions.

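### The 90% power is for one test on 221 patients. The claim needs both the ITT and the per-protocol analysis to pass, and power for that rule is not shown.

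*Combined protocol and SAP*

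**What the plan says.** Protocol D.8 and the SAP section Sample Size Rationale power one comparison of mean RMDQ at 12 weeks, "which amounts to a one-sided, two-sample t-test". The inputs are a margin of 2 points, one-sided alpha 0.025, and "postulating a true difference in group means of 0 and a standard deviation of the outcome of 4.5 in both groups". The result is that "we will have 90% power to detect non-inferiority with a total sample size of 221 patients, or 128:93". A 20% drop-out rate then takes enrolment to 278 (160:118) in the protocol and 277 (160:117) in the SAP.

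The decision rule is in D.9, Analysis of Endpoints, and is repeated in the SAP under Definitions of the Analytical Sets. Non-inferiority is declared "only if AI-CBT is shown to be non-inferior using both the intention-to-treat and per-protocol analysis sets". Per protocol means four or more completed sessions, IVR or live, and the text leaves that definition open to review by the Expert Panel.

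Neither document gives an expected per-protocol size, an allowance for per-protocol exclusions, or the power of the two-part rule. Neither says whether 221 is the ITT or the per-protocol set, or what kind of drop-out the 20% describes.

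**The concern.** The headline power and the success criterion refer to different events. The 90% is the probability that one test passes with 221 patients. The trial succeeds only if two tests pass, and the second may use fewer patients.

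Outcomes are collected by telephone survey, separately from therapy. A patient who stops after two sessions can still give a 12-week RMDQ, and then counts in ITT but not per protocol. If the 20% is used up by missing outcomes, nothing is left for such patients.

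Two things are at stake. The stated power may be somewhat too high for the claim the trial will make. And if the per-protocol set turns out smaller than 221, a failed per-protocol test could reflect lost precision rather than a worse treatment, with no stated expectation to judge it against.

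**Working it through.** **Inputs.** From D.8 and the SAP: margin 2, SD 4.5, true difference 0, one-sided alpha 0.025, 128:93 evaluable, 20% drop-out. From D.9: both analyses must pass. Assumed, because the documents give no figure: the per-protocol share, equal exclusion in both arms, and the same true difference (0) and SD in both sets.

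**1. Reproduce the plan's figure.**
- SE = 4.5 × √(1/128 + 1/93) = 0.613.
- 2/0.613 − 1.960 = 1.302, and Φ(1.302) = 90.4%. The noncentral t gives 90.1%.
- 128/0.8 = 160 and 93/0.8 = 116.25, rounded up to 117, total 277. The SAP figure follows directly. The protocol's 278 differs by one patient, with negligible effect here.

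**2. Power of the two-part rule.** The per-protocol set is nested in ITT, so the two estimates have correlation ρ = √(n_PP/n_ITT). Joint power is Φ₂(c_ITT, c_PP; ρ), with c = 2/SE − 1.960 for each set.

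Worked case, 90% of the 221 per protocol: SE_PP = 0.613/√0.9 = 0.646; c_PP = 2/0.646 − 1.960 = 1.135; ρ = √0.9 = 0.949; Φ₂(1.302, 1.135; 0.949) = 86.0%.

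**3. Per-protocol exclusions on top of the 20%** (ITT = 221 observed patients):

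| Per-protocol share of 221 | n | Per-protocol test alone | Joint power |
|---|---|---|---|
| 100% | 221 | 90.4% | 90.4% (t: 90.1%) |
| 95% | 210 | 88.9% | 87.9% |
| 90% | 199 | 87.2% | 86.0% |
| 80% | 177 | 83.1% | 81.8% |

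**4. The 20% covers per-protocol exclusions** (all 277 give outcomes, ITT test 95.5%):

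| Per protocol | Per-protocol test alone | Joint power |
|---|---|---|
| 221 (128:93) | 90.4% | 89.7% |
| 85% of 277 | 92.1% | 91.4% |
| 90% of 277 | 93.4% | 92.8% |

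The tables use the normal approximation. Simulated pooled t-tests agree within about 0.7 points; for 277 with 221 per protocol they give about 89.4%.

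**5. Baseline adjustment.** If 4.5 is an unadjusted SD and r is the correlation of baseline with 12-week RMDQ, the residual SD is 4.5 × √(1 − r²): 4.29, 4.12 and 3.90 for r = 0.3, 0.4 and 0.5. With 80% of the 221 per protocol, joint power by the formula in step 2 is 85.4%, 88.2% and 91.5%. Simulated t-tests at these residual SDs give 84.9%, 87.6% and 91.3%.

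**The case against.** The strongest reply is that nothing is miscalculated and the design may well have its 90%. If drop-outs are the patients who both stop therapy early and give no outcome, ITT and per protocol are the same 221 and joint power equals the single-test figure. If nearly everyone gives an outcome and 85% to 90% are per protocol, joint power exceeds 90%. The threshold is low (four of ten sessions, IVR counted), and section D.6 reports more than 90% completion of IVR sessions in the team's related trial. The two-part rule is also conservative and costs no type I error. All of this stands. It means a shortfall is possible rather than demonstrated.

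Three stronger readings are tempting, and the documents do not support them.
- A reader might infer that the design lacks 90% power for its own claim. That follows only if per-protocol exclusions come on top of the 20%, which the plan leaves undefined.
- A reader might multiply 0.9 × 0.9 and get 81%. That is for independent tests. These are nested and highly correlated, so requiring both costs little by itself. The loss comes from a per-protocol set smaller than 221.
- A reader might take the SAP's remark that "many Veterans drop out of treatment early" as a forecast for this trial. It describes existing VA services and cites intolerance of in-person visits as one reason. Here both arms are treated by telephone or IVR, and no drop-out rate from therapy is projected.

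What the reply does not supply is the missing statement. At 221 there is almost no reserve, so whether the rule has 90% power depends on an allowance that the plan has not defined.

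**Conclusion.** The point holds as a gap in what is shown. The stated 90% is correct for one analysis with 221 patients. For the rule that decides the trial, it holds exactly or nearly only if the 20% allowance also absorbs per-protocol exclusions: 90.1% if the two sets coincide, about 89% to 90% with 277 outcomes and 221 per protocol, and about 91% to 93% if 85% to 90% of 277 are per protocol. If exclusions are additional, joint power is about 88%, 86% or 82% at 5%, 10% or 20% of the 221.

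These figures assume a true difference of zero and SD 4.5 in both sets, and equal exclusion by arm. Unequal exclusion, or a different true effect among patients who complete four sessions, would change them. The 277-outcome figures require outcomes that are actually observed, because imputed values do not supply the same information. The exclusion rates are illustrations, not estimates from the documents.

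**What to change.** In D.8 and the SAP's Sample Size Rationale:
1. Say that 90% is the power of a single analysis with 221 patients.
2. State whether the 20% covers missing 12-week outcomes, fewer than four sessions, or both.
3. State the assumed per-protocol fraction, and replace the headline with the joint power for that fraction.

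In D.9 and the SAP's Analysis of Endpoints, make the 12-week primary comparison in both sets an analysis adjusted for baseline RMDQ. That variable is already collected and is already a covariate in the planned mixed model. State also whether 4.5 is an unadjusted SD. If it is, joint power at 20% further exclusion becomes about 85%, 88% or 91% for an assumed baseline correlation of 0.3, 0.4 or 0.5. Full recovery is therefore possible but not guaranteed, and the plan should state the correlation it relies on.

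The cost is wording in two documents, plus one change to the primary model that should be fixed before group assignments are unblinded. No extra enrolment is asked for. The stated power may become slightly less favourable.
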